#### 6.6.3.4. Dose Reductions, Interruptions, and Delays

##### **Dose Reduction**

A dose reduction is defined as a nonzero dose that is less than the planned dose. The planned dose is the same as the prior dose except for elranatamab at C0D4 and C0D8.

For each study treatment, the number and percentage of participants with at least 1 dose reduction as well as a breakdown of dose reductions (1/2/3/ ≥4) will be summarized by dose cohort (dose escalation part) and treatment arm (dose expansion). In addition, the number and percentage of participants with at least 1 dose reduction due to an AE will also be summarized.

## **Dose Interruption**

An interruption is defined as missing a scheduled dose based on the planned dosing frequency (QW or Q2W). For each study treatment, the number and percentage of participants with dose interruptions as well as a breakdown of dose interruptions (1/2/3/ ≥4) will be summarized by cohort and overall. In addition, the number and percentage of participants with at least 1 dose interruption due to AE will also be summarized. Percentages will be calculated based on the total number of participants in the Safety Analysis Set.

## **Dose Delay**

For elranatamab, a dose delay will be derived based on study drug administration date and will be grouped into the following categories based on the deviation of the actual to the planned treatment administration day (relative to the previous treatment administration date):

- No delay;
- 1-3 days delay;
- 4-6 days delay;
- 7 or more days delay (only in the Q2W schedule).

The number and percentage of participants with delayed study drug administration and maximum length of delay, ie, the worst case of delay if participants have multiple dose delays will be summarized by cohort, as applicable.

Dose delay is not applicable to lenalidomide or dexamethasone.

### **6.6.4. Concomitant Medications and Nondrug Treatments**

See [Section 6.5.4 of the master SAP](#) for summaries of concomitant medications and nondrug treatments.

### **6.6.5. Subsequent Anticancer Therapies**

See [Section 6.5.5 of the master SAP](#) for summaries of subsequent anticancer therapies.

### **6.7. Safety Summaries and Analyses**

See [Section 6.6 of the master SAP](#) for safety summaries and analyses.

## **7. INTERIM ANALYSES**

### **7.1. Introduction**

There are interim safety assessments planned for this sub-study.

For both dose escalation and dose expansion parts of the sub-study, an internal safety review team will review safety and tolerability data on an ongoing basis for the interim safety assessments.

## 7.2. Interim Analyses and Summaries

### 7.2.1. Interim Safety Assessments

An internal safety review team will review cumulative safety data during the study conduct. In addition, the incidence of the following events will each be monitored by the Sponsor throughout the study. The review results and decisions will be documented in the study TMF.

- Grade 3-4 CRS;
- Grade 3-4 ICANS;
- Grade 4 treatment-related non-hematologic events (excluding CRS and ICANS);
- Grade 3-4 treatment-related GBS/GB-like AEs;
- Grade 4 treatment-related sensory neuropathy/other IR neurologic AEs (excluding ICANS);
- Grade 3-4 treatment-related motor neuropathy;
- Grade 5 events.

If the number of participants observed to have such identified events exceeds a prespecified threshold across dose levels, the sub-study will be placed on a temporary enrollment hold by the Sponsor. During any temporary enrollment hold, no new participants can be enrolled, nor can any newly enrolled participants start study intervention. Participants who have already started study intervention may continue treatment only if the benefit/risk assessment for the participant is judged to be positive by the investigator in consultation with the sponsor.

The criteria for placing the sub-study on temporary hold for safety reasons are based on Bayesian posterior probabilities. Using a non-informative Beta (0.5, 0.5) prior distribution, if the number of participants observed to have Grade 3 or 4 CRS results in a  $\geq 0.90$  posterior probability that the true Grade 3 or 4 CRS rate exceeds 20%, the sub-study will be put on a temporary hold. Separate but similar criteria will be used for participants with Grade 3-4 ICANS and treatment-related Grade 4 non-hematologic events (excluding CRS and ICANS). [Table 6](#) summarizes the minimum number of participants with such identified events that would meet the above criteria.

**Table 6. Identified Events That Would Prompt Temporary Enrollment Hold**

Number of Evaluable Participants	8-11	12-14	15-18	19-22	23-26	27-30	31-34
Minimum number of participants with Grade 3-4 CRS events that would lead to a temporary enrollment hold*	4	5	6	7	8	9	10
Minimum number of participants with Grade 3-4 ICANS events that would lead to a temporary enrollment hold*	4	5	6	7	8	9	10
Minimum number of participants with Grade 4 treatment-related non-hematologic events (excluding CRS and ICANS) that would lead to a temporary enrollment hold*	4	5	6	7	8	9	10

Prior distribution: Beta (0.5,0.5)

Criteria for 35+ or more evaluable participants will be calculated such that the sub-study will be put on temporary hold if the posterior probability that the true event rate exceeds 20% is greater than or equal to 0.90.

Evaluable participants are defined as those having an identified event or those without such an event who have been followed for at least 35 days from first dose.

\* The study will be put on temporary hold as soon as the minimum number of evaluable participants with the identified AEs has reached the threshold (eg, if there are 4 participants experiencing the identified AEs out of the first 6 evaluable participants, the study will be put on hold). A minimum of 4 events are required to trigger a temporary hold.

The criteria for placing the study on temporary hold for the following safety reasons are based on Bayesian posterior probabilities using a non-informative Beta (0.5, 0.5) prior distribution. Specifically,

- If the number of evaluable participants observed to have treatment-related Grade 3-4 GBS/GB-like AEs results in a posterior probability that the true rate of such events exceeding 3% is  $\geq 0.80$ , the study will be put on a temporary hold;
- If the number of evaluable participants observed to have treatment-related Grade 4 sensory neuropathy/other IR neurologic AEs (excluding ICANS) or treatment-related Grade 3-4 motor neuropathy results in a posterior probability that the true rate of such events exceeding 10% is  $\geq 0.80$ , the study will be put on a temporary hold.

[Table 7](#) summarizes the minimum number of evaluable participants with such identified events that would meet the above criteria.

**Table 7. Minimum Number of Participants with Identified Treatment-Related Events That Would Prompt Temporary Enrollment Hold (GBS/GB-like AEs, Peripheral Neuropathy/IR Neurologic AEs)**

Number of Evaluable Participants	20-39			-	-
Minimum number of participants with Grade 3-4 treatment-related GBS/GB-like events that would lead to a temporary enrollment hold*	2			-	-
Number of Evaluable Participants	6-11	12-19	20-27	28-35	36-43
Minimum number of participants with Grade 4 treatment-related sensory neuropathy /IR neurologic AE (excluding ICANS) or Grade 3-4 treatment-related motor neuropathy events that would lead to a temporary enrollment hold**	2	3	4	5	6

Prior distribution: Beta (0.5,0.5).

Evaluable participants are defined as those who have received at least 1 dose of study treatment having an identified event or those without such an event who have been followed for at least 28 days from first dose.

\*The study will be put on temporary hold as soon as the minimum number of evaluable participants with the identified AEs has reached the threshold (eg, for GBS/GB-like AEs, if there are 2 participants experiencing the identified AE out of the first 10 evaluable participants, the study will be put on hold). A minimum of 2 events are required to trigger a temporary hold.

\*\* The study will be put on temporary hold as soon as the minimum number of evaluable participants with the identified AEs has reached the threshold (eg, if there are 2 participants experiencing the identified AEs out of the first 4 evaluable participants, the study will be put on hold). A minimum of 2 events are required to trigger a temporary hold.

In addition, the study will be put on temporary hold if any of the following criteria are met:

- 1 Grade 5 event of CRS (by ASTCT criteria);
- 1 Grade 5 event of ICANS (by ASTCT criteria);
- 1 Grade 5 treatment-related peripheral neuropathy or IR neurologic event;
- Any 2 treatment-related Grade 5 events (excluding CRS and ICANS and peripheral neuropathy/IR neurologic event).

If number of evaluable participants go beyond the one listed in the tables, number of identified events that would prompt temporary hold will be updated accordingly based on the same Bayesian criteria.

090177e1993a4a6d\Approved\Approved On: 31-Jan-2022 16:54 (GMT)

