## 4. ANALYSIS SETS (POPULATIONS FOR ANALYSIS)

For purposes of analysis, the following analysis sets are defined:

Participant Analysis Set	Description
DLT-Evaluable Analysis Set	
The DLT-evaluable analysis set will include all enrolled participants who receive at least 1 dose of the study intervention in the Phase 1b part of the study and either experience DLT(s) or complete the DLT observation period without DLT. Participants without DLTs who receive less than the minimum requirement of the planned doses of each IP for reason other than treatment-related toxicity are not evaluable for DLTs.
 
The DLT observation period is 35 days from Cycle 0 Day 1 through Cycle 1 Day 28.

090177e196913362\Approved\Approved On: 19-Mar-2021 12:41 (GMT)

	
The minimum required exposure for DLT evaluability is defined as follows:
 
 
• For PF-06863135 (all sub-studies): 4 out of 5 planned doses during the DLT observation period. Participants must be able to receive the full dose on Cycle 1 Day 1 (-1/+3 dosing window) and not require any dose reductions during the DLT observation period;
 
• For nirogacestat (sub-study A): at least 75% of the planned doses and not require any dose reductions during the DLT observation period.
 

Safety Analysis Set	The safety analysis set will include all enrolled participants who received at least 1 dose of study intervention.
PK Analysis Set	
The PK analysis set will include all participants in the safety analysis set who have at least 1 post-dose concentration measurement.
 
The PK parameter analysis set will include all participants in the safety analysis set who have at least one of the PK parameters of interest for PF-06863135.

Immunogenicity Analysis Set	The immunogenicity analysis set will include all participants in the safety analysis set who have at least 1 sample tested for ADA.
Biomarker Analysis Set	
The biomarker analysis set will include all participants in the safety analysis set who have at least 1 baseline biomarker assessment.
 
Analysis sets will be defined separately for biomarkers based on blood, and bone marrow samples.

PRO Analysis Set	The PRO analysis set will include all participants in the safety analysis set who completed a baseline (last PRO assessment prior to or on the first dose of study intervention) and at least 1 post-baseline PRO assessment.

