### Dose Escalation Design:

[figure not shown]
Approximately 3-6 DLT-evaluable participants will be treated at each dose level of the combination therapy. If DL1 is tolerated, two cohorts (DL2a and DL2b) will be initiated in parallel and arm allocation for participants follows an alternative allocation scheme. DL2a and DL2b must be considered tolerable before DL3 can be opened. Before moving to the next dose level, the safety data will be evaluated by a dose level review committee once evaluable participants have been followed for a minimum of 42 days after the first dose of elranatamab (14 days from the first elranatamab dose + first 28 days following the first dose of the combination of elranatamab, lenalidomide, and dexamethasone).

Dose escalation/de-escalation decisions will be guided by a BLRM approach to determine the MTD of elranatamab when administered in combination with lenalidomide and dexamethasone. However, other evidence such as safety data beyond DLT window, clinical activity, PK, and pharmacodynamics data will also be evaluated in determining the RP2D. The RP2D will be determined with agreement between the investigators and the Sponsor at the dose level review committee.

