### **3. ENDPOINTS AND BASELINE VARIABLES: DEFINITIONS AND CONVENTIONS**

#### **3.1. Primary Endpoints**

##### **3.1.1. Dose Escalation**

The primary endpoint of the dose escalation part is the DLTs during the DLT observation period, which is the first 42 days from Cycle 0 Day 1 through Cycle 1 Day 28 of study intervention.

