A minimum of 2 days should be maintained between the 2 step-up doses (C0D1 and C0D4) and a minimum of 3 days between C0D4 and the first full dose (C0D8); a minimum of 6 days is required between doses thereafter.

The summary of treatment exposure to elranatamab will include the following information:

- Treatment duration (weeks);
- Number of cycles started per participant (mean, median, min, max);
- Number and percent of participants starting a cycle (any cycle, cycle 0, 1, 2, 3, 4, 5, 6, 7, 8, 9, 10, 11, >=12 cycles);
- Total cumulative dose (mg);
- Overall dose intensity (mg/week);
- Overall relative dose (%);
- Overall relative dose intensity (%);
- Number and percent of participants after 6 cycles who switched from QW to Q2W;
- Number and percent of participants, among those switching from QW to Q2W, who switched back to QW.

The treatment duration of elranatamab (in weeks) during the study for a participant is defined as:

- Treatment duration (weeks) = (last dose date – first dose date + 1)/7

Planned treatment duration and intended treatment duration are needed to calculate dose intensity (DI) and relative dose intensity (RDI). It is defined as follows:

- Planned treatment duration (weeks) = 2(2 week for Cycle 0) + number of cycles started × 4 - (number of weeks in the last cycle after permanent treatment discontinuation or data cutoff for those on-treatment).
- Intended treatment duration (weeks) = (last zero/non-zero dose date – first dose date)/7 + 1 if on QW or 2 if on Q2W

**Note:** If C0D4 is the last visit and dose is given at this visit, duration is 1 week.

The planned dose for a given cycle is defined as:

- Cycle 0:
  - Planned dose (mg/cycle) = Planned priming dose(s) per protocol during C0
- After Cycle 0:
  - If the participant is on QW dosing schedule for the cycle:  
Planned dose (mg/cycle) = Full dose × 4
  - If the participant is on Q2W dosing schedule for the cycle:  
Planned dose (mg/cycle) = Full dose × 2

**Note:** Full dose=44 or 76 mg depends on DLs. For the last cycle, subtract planned doses after a participant permanently discontinues treatment or data cutoff for those on-treatment.

The total planned dose is the sum of the total planned dose across all cycles.

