### 6.6.3.2. Exposure to Lenalidomide

Starting on Cycle 1, the first dosing of the two combination partners (lenalidomide and dexamethasone) will be initiated.

Escalating doses of 15 mg or 25 mg of lenalidomide PO QD will be administered on Days 1-21 of each 28-day cycle for all cycles. De-escalating dose of 10 mg is permitted, depending on the dose levels being evaluated.

The summary of treatment exposure to lenalidomide will include the following information:

- Treatment duration (weeks);
- Total cumulative dose (mg);
- Overall dose intensity (mg/week);
- Overall relative dose intensity (%).

The treatment duration of lenalidomide (in weeks) during the study for a participant is defined as:

- Treatment duration (weeks) = (last dose date - first dose date + 1)/7

Planned treatment duration, intended treatment duration, planned dose and planned DI is needed to calculate DI and RDI. The planned treatment duration is defined as:

- Planned treatment duration (weeks) = (number of cycles started x 4) - (number of weeks in the last cycle after permanent treatment discontinuation or data cutoff for those on-treatment).
- Intended treatment duration (weeks) = (last zero/non-zero dose date – first dose date)/7 + 1
- Planned dose (mg/cycle) = Full dose (mg) × 21, Full dose=15, 25 or 10 depending on DL.

**Note:** For last cycle, subtract planned doses after a participant permanently discontinues treatment or data cutoff for those on-treatment.

The total planned dose is the sum of the total planned dose across all cycles.

The total cumulative dose (mg) of Lenalidomide is the sum of the actual dose levels that the participant received during the study (ie, total dose administered [mg]).

The overall planned DI is defined as:

- Overall Planned DI (mg/week) = Total planned dose (mg)/(planned treatment duration in weeks).

The overall DI and RDI of lenalidomide will be calculated for each participant during the study.

- Overall DI (mg/week) = Total cumulative dose (mg)/ Intended treatment duration (weeks);
- Overall RD (%) = [Total cumulative dose (mg) / Total planned dose (mg)] × 100;
- Overall RDI (%) = [Overall DI (mg/week) / Overall Planned DI (mg/week)] × 100.

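### Sub-study B's Table 6 hold rule counts event-free participants as evaluable at 35 days, although that sub-study's own observation window is 42 days

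*SAP*

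**What the plan says.** **Observation window.** Sub-study B SAP Section 3.1.1 defines the DLT observation period, "which is the first 42 days from Cycle 0 Day 1 through Cycle 1 Day 28 of study intervention". Section 2.2 (Dose Escalation Design) builds the 42 days as "14 days from the first elranatamab dose + first 28 days following the first dose of the combination", and makes 42 days the minimum follow-up before the dose level review. Section 6.6.3.2 adds: "Starting on Cycle 1, the first dosing of the two combination partners (lenalidomide and dexamethasone) will be initiated".

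**Hold rules.** Section 7.2.1 has two sets of Bayesian hold rules, each with its own evaluability footnote:

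- Table 6 (Grade 3-4 CRS, Grade 3-4 ICANS, Grade 4 treatment-related non-hematologic events): participants with an event count as evaluable, together with "those without such an event who have been followed for at least 35 days from first dose".
- Table 7 (GBS/GB-like events and neuropathy/immune-related neurologic events): event-free participants count once they have been "followed for at least 28 days from first dose".

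**Comparison.** Master SAP Section 4 states: "The DLT observation period is 35 days from Cycle 0 Day 1 through Cycle 1 Day 28". The footnote to the master SAP's hold table (its Table 6, Section 7.2.1) uses the same 35-day wording as Sub-study B's Table 6.

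**The concern.** In the master SAP, an event-free participant enters the hold denominator exactly when the DLT window closes. Sub-study B lengthened Cycle 0 from one week to two and moved its DLT window to 42 days, but its Table 6 footnote still says 35. A participant at day 36 is too early for the dose level review, yet already counts as a non-event in the hold rule.

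What is at stake is the sensitivity of the hold rule to toxicity of the full combination. The expansion part has safety as its primary objective and no decision rule of its own (Section 5.1.2.2). Apart from the Grade 5 triggers, these tables are its prespecified quantitative safety triggers.

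**Working it through.** **1. Calendar.** C0D1 is day 1 and Cycle 0 lasts 14 days, so C1D1 = day 15.

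| Day from first dose | Cycle day | Combination days observed | Share of the 28 |
|---|---|---|---|
| 28 (Table 7) | C1D14 | 14 | 50% |
| 35 (Table 6) | C1D21 | 21 | 75% |
| 42 (DLT window) | C1D28 | 28 | 100% |

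Measured against the whole 42-day window, the part not yet seen is 7/42 = 17% at day 35 and 14/42 = 33% at day 28. Section 6.6.3.3 also lists dexamethasone in Cycle 0, whereas Table 5 and Section 6.6.3.2 start it on C1D1; those passages need reconciling. Lenalidomide starts on C1D1, so day 15 stands as the start of the full combination.

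**2. The plan's thresholds reproduce.** With prior Beta(0.5, 0.5) and r events in n evaluable, the posterior is Beta(0.5 + r, 0.5 + n − r). The threshold is the smallest r with P(rate > p0) at or above the cutoff.

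- Table 6 (p0 = 20%, cutoff 0.90): 4, 5, 6, 7, 8, 9, 10 events for n = 8-11, 12-14, 15-18, 19-22, 23-26, 27-30, 31-34. Every band matches.
- Table 7 neuropathy row (10%, 0.80): 2, 3, 4, 5, 6 events for n = 6-11, 12-19, 20-27, 28-35, 36-43. Every band matches.
- Table 7 GBS row (3%, 0.80): 2 events for n = 17-39, against a printed 20-39. The upper bound matches, and the footnote already triggers a hold at 2 events for smaller n.

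The thresholds are sound. Only the definition of n is in question.

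**3. Direction.** Participants with an event count at once under either definition, so r is the same. Event-free participants at day 42 are a subset of those at day 35, so n is the same or smaller under a 42-day rule. The threshold does not fall as n rises. Hence any hold under the 35-day rule is also a hold under the 42-day rule, at the same time or earlier.

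**4. Band edges.** One additional event-free participant changes the outcome at these points:

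| Rule | Hold | No hold |
|---|---|---|
| Table 6 (20%, 0.90) | 4/11: 0.906 | 4/12: 0.874 |
| | 5/14: 0.922 | 5/15: 0.897 |
| | 6/18: 0.915 | 6/19: 0.893 |
| Table 7 neuropathy (10%, 0.80) | 2/11: 0.827 | 2/12: 0.797 |
| | 3/19: 0.810 | 3/20: 0.786 |

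These edges lie within the planned size: up to 24 in escalation plus 20 − 6 = 14 further participants in expansion, 38 in all.

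**5. Size in hold probability.** Simulation, 3,000 trials per setting. Assumptions, none of them from the documents: 38 participants, mean gap 7 or 14 days between entries, events uniform over the 42 days, over the combination phase only, or over Cycle 0 only. Ranges of the chance of a hold during enrollment:

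| Rule | True rate | Current rule | 42-day rule |
|---|---|---|---|
| Table 6 (35 days) | 20% | 0.30-0.44 | 0.32-0.46 |
| Table 6 (35 days) | 30% | 0.75-0.84 | 0.75-0.86 |
| Table 7 neuropathy (28 days) | 10% | 0.45-0.54 | 0.47-0.59 |
| Table 7 neuropathy (28 days) | 20% | 0.91-0.94 | 0.92-0.95 |

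Compared setting by setting, the largest loss is about 4 points for Table 6 (0.309 against 0.350) and about 6 for Table 7 (0.468 against 0.531). The two rules were simulated on separate draws, so a difference near a hold probability of 0.35 has a standard error of about √(2 × 0.35 × 0.65 / 3000) = 0.012. The few slightly negative differences are noise. A second set of runs, with a 42-day wait between escalation cohorts, gave losses of 0.3-2.5 points (Table 6, true rate 20-30%) and 0.7-4.9 points (Table 7, 10-20%).

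**The case against.** **No stated rule is broken.** Nothing in the documents says that evaluability for a hold must equal the DLT window. This stands: the point is an unexplained mismatch. The identical wording makes carry-over from the master SAP likely for the 35 days, but that remains an inference, and a rationale could sit in the sub-study protocol, which was not available for this review.

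**The carry-over argument does not reach Table 7.** Sub-study A's neurologic table (its Table 8) also uses 28 days, against a window of approximately 35. A reader might infer that Table 7's figure is the same slip. The documents do not support that; the case there rests only on the 14 of 28 combination days observed.

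**A hold cannot be cancelled.** A reader of the band-edge figures might infer that one early-counted participant undoes a hold. The footnotes put the hold in force as soon as the threshold is reached, and a later twelfth participant does not lift it. The figures matter only if that participant is between day 35 and day 41 when the deciding event occurs. From day 42 on, both definitions give 4/12.

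**The rate is not underestimated overall.** A reader might also infer a general dilution. Monitoring is continuous, and a later event still moves the participant into the numerator. Events also count at once while event-free participants wait, which pushes the observed rate up. In the simulation, the mean observed rate at mid-enrollment under the current rules was about equal to or above the true rate (for Table 6 at a true 20%, 0.204 to 0.244). The loss exists only relative to a 42-day rule.

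**Other safeguards exist.** Escalation waits the full 42 days and uses the BLRM with a review committee, the Grade 5 triggers need no denominator, and cumulative safety review is ongoing. For events clustered in Cycle 0, where the SAP places CRS mitigation, day 35 already covers the risk period. This limits the weight of the point but does not explain the 35 days.

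**Conclusion.** The point holds for Table 6 as a mismatch between the hold rule's evaluability period and the sub-study's own 42-day window. Its direction is certain: relative to a 42-day definition, the denominator is never smaller and a hold is never earlier. Its size is small and each early count lasts at most 7 days (14 for Table 7). Under the assumed accrual and event timing, the loss in hold probability is about 0 to 6 points across both tables and 0 to about 4 for Table 6. At rates well above the limits (30% for Table 6, 20% for Table 7), it was at most about 2.4 points. The practical weight is greater for Grade 4 non-hematologic events arising late in Cycle 1 than for CRS.

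For Table 7 the conclusion is weaker: 28 days is short for a combination that starts on day 15, but it follows a figure used elsewhere in the program and needs a reason rather than a presumed correction.

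**What to change.** - **Table 6 footnote, Sub-study B:** define event-free evaluability as at least 42 days from first dose, to match Sections 2.2 and 3.1.1. Keep the printed thresholds.
- **Table 7 footnote, Sub-study B:** either align with the 42-day window or state, for each event type, why 28 days is enough.

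The cost is footnote wording. The evaluable count lags by 7 days for Table 6 (14 for Table 7 if aligned). A hold becomes slightly more likely, including when the true rate is only at the limit: in the simulation at 20%, 0.32-0.46 instead of 0.30-0.44.
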